### 2.2. Secondary Objective(s)

The key secondary objectives of Study 2 are:

- To demonstrate that ZX008 0.2 mg/kg/day is superior to placebo as adjunctive therapy in the treatment of Dravet syndrome based on change in the frequency of convulsive seizures between baseline and T+M.
- To demonstrate that the ZX008 0.2 and 0.8 mg/kg/day dose groups are (independently) superior to placebo on the following endpoints:
  - The proportion of subjects who achieve a  $\geq 50\%$  reduction from baseline in convulsive seizure frequency.
  - The longest convulsive seizure-free interval.

Additional Secondary Objectives:

- To demonstrate that the ZX008 0.2 and 0.8 mg/kg/day dose groups are (independently) superior to placebo on the following endpoints:
  - The number of convulsive seizure-free days.
  - The proportion of subjects who achieve  $\geq 25\%$ , or  $\geq 75\%$ , or 100%, or near seizure-free (ie, at most 1 convulsive seizure) reductions from baseline in convulsive seizure frequency.
  - The change from baseline in non-convulsive seizure frequency.
  - The change from baseline in convulsive + non-convulsive seizure frequency
  - The incidence of rescue medication usage
  - The incidence of hospitalization to treat seizures
  - The incidence of status epilepticus.
- To demonstrate that the ZX008 0.2 and 0.8 mg/kg/day dose groups are (independently) superior to placebo on the following endpoints:
  - Clinical Global Impression – Improvement rating, as assessed by the principal investigator.
  - Clinical Global Impression – Improvement rating, as assessed by the parent/caregiver.
  - The change from baseline in the Quality of Life in Childhood Epilepsy (QOLCE) score.
  - The change from baseline in the Pediatric Quality of Life Inventory™ (PedsQL) score.
  - The change from baseline in the PedsQL Family Impact module score.
  - The change from baseline in the QoL of the parent/caregiver using the EQ-5D-5L scale.
  - The change from baseline in the affective symptoms of the parent/caregiver using the Hospital Anxiety and Depression Scale (HADS).

The safety objective of the Study 2 is:

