#### 4. Key Secondary Efficacy Endpoints

The key secondary endpoints of Study 2 are:

- Change from baseline in the mean convulsive seizure frequency (MCSF) in T+M in the ZX008 0.2 mg/kg/day group compared to the placebo group.  
The change from baseline in MCSF for the ZX008 0.2 mg/kg/day group will be analyzed using the same methods as the primary analysis.
- ZX008 0.2 and 0.8 mg/kg/day dose groups compared independently versus placebo on the
  - The proportion of subjects who achieve a  $\geq 50\%$  reduction from baseline in convulsive seizure frequency.  
The proportion in each ZX008 treatment group will be compared independently to placebo using logistic regression analysis.
  - The longest convulsive seizure-free interval during T+M.  
Each ZX008 treatment groups will be compared to placebo on the longest interval using an independent Wilcoxon rank-sum test.

The additional secondary endpoints are:

- ZX008 0.2 and 0.8 mg/kg/day dose groups compared independently versus placebo on the
- The number of convulsive seizure-free days.
  - The proportion of subjects who achieve  $\geq 25\%$ ,  $\geq 75\%$ , or 100% reductions from baseline in convulsive seizure frequency.
  - The proportion of subjects with at most 1 (ie,  $\leq 1$  convulsive seizure) during T+M.
  - The change from baseline in non-convulsive seizure frequency.
  - The change from baseline in convulsive + non-convulsive seizure frequency
  - The incidence of rescue medication usage
  - The incidence of hospitalization to treat seizures
  - The incidence of status epilepticus.
  - Clinical Global Impression – Improvement rating, as assessed by the principal investigator.
  - Clinical Global Impression – Improvement rating, as assessed by the parent/caregiver.
  - The change from baseline in the Quality of Life in Childhood Epilepsy (QOLCE) score.
  - The change from baseline in the Pediatric Quality of Life Inventory™ (PedsQL) score.
  - The change from baseline in the PedsQL Family Impact module score.
  - The change from baseline in the QoL of the parent/caregiver using the EQ-5D-5L scale.

This document is confidential.

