### 5.3. Modified Intent-to-Treat (mITT) Population

The mITT Population is defined as all randomized subjects who receive at least one dose of ZX008 or placebo and for whom at least one week of diary data are available. Subjects will be analyzed according to the treatment group to which they were randomized. The primary comparison of ZX008 0.8 mg/kg/day to placebo, as well as key secondary analyses, will be performed on the mITT Population.

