#### **Missing Data Due to Dropouts:**

The issue of missing data has gained much attention subsequent to the National Academy of Science Report on the Treatment and Handling of Missing Data (NAS Report, 2010). Within the context of the studies, missing data arise from two sources: intermittent missing assessments (such as missing diary data), and as a result of dropouts prior to the end of the titration + maintenance periods.

In Study 1, only 2 (out of the 119) subjects had more than 7 days of missing diary data while on treatment (before dropout). The rates of dropout in the pivotal trials was 7.56% (9/119) in Study 1. Dropouts that are related to treatment response leave the possibility that the analysis of efficacy endpoints, which relies on assumptions of data being missing at random (MAR), may be violated. It is possible, though, that data may be missing not at random (MNAR). Differential dropouts leading to missing assessments may thus affect the inference on the primary endpoint.

The primary analysis method, in so far as it uses the convulsive seizure frequency averaged over the entire treatment period, in effect, assumes that a dropout would have followed the mean profile experienced up to that point in time when the subject dropped out from the study. Alternative, explicit, ways of addressing the issue of missing seizure data due to dropouts may be considered. (Kenward 2015) Two methods were chosen for minimal impact on variability of estimates as well as their simplicity.

It is assumed that the **planned duration** of T+M for Study 1 and Study 2 subjects is 14 weeks (98 days).

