### 8.1. Primary Efficacy Endpoint and Analysis

The primary efficacy endpoint is the change in the mean convulsive seizure frequency (MCSF) per 28 days between the Baseline and T+M periods. For each subject, the CSF will be calculated from all available data collected during the Baseline and T+M Periods, and the treatment group mean convulsive seizure frequency per 28 days (MCSF) will be calculated for the baseline and T+M period.

The baseline period is the 42 days immediately preceding the Randomization visit and the T+M period is planned for 14 weeks. However, actual durations will be computed for each subject based on the individual subject's start and stop dates for each period, except that if the baseline period is longer than 42 days, the average for the baseline period will be taken over the 42 days immediately preceding the Randomization visit.

The convulsive seizure frequency will be counted from the daily diary records provided by the Subject or Parent/Caregiver.

For any individual subject, the convulsive seizure frequency per 28 days during the baseline period ( $CSF_B$ ) will be derived as follows:

$$CSF_B = \frac{28 \times \text{Total number of convulsive seizures during the Baseline Period}}{\text{Total number of days in the Baseline Period with nonmissing diary data}}$$

For each treatment group, the mean is obtained by averaging over the subjects in the treatment group.

Similarly, for each subject, the convulsive seizure frequency per 28 days for the T+M period ( $MCSF_{T+M}$ ) is derived as below:

$$CSF_{T+M} = \frac{28 \times \text{Total number of convulsive seizures in the T + M period}}{\text{Total number of days in the T + M period with nonmissing diary data}}$$

The percentage change from baseline for any individual subject will be estimated by

$$(CSF_{T+M} - CSF_B) * 100 / CSF_B$$

The difference from baseline will be estimated by  $CSF_{T+M} - CSF_B$ .

Corresponding treatment group means are designated with "M" preceding the quantity. For each treatment group, descriptive statistics for MCSF during baseline, T+M and M only, as well as the differences and % changes from baseline, will include the number of observations, mean, standard deviation, median, minimum and maximum, overall and by age group (<6 years, ≥6 years).

This document is confidential.

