## Statistical Analysis Plan

Sponsor: Zogenix International Limited; Protocol No.: ZX008 Study 2 (ZX008-1501 and ZX008-1502)

- The proportion achieving a  $\geq 25\%$  reduction from baseline in convulsive seizures will be analyzed for both treatment groups (ZX008 0.2 mg/kg/day and ZX008 0.8 mg/kg/day) comparing independently with placebo, using the same methods employed for the  $\geq 50\%$  reduction from baseline endpoint.
- The proportion achieving a  $\geq 75\%$  reduction from baseline in convulsive seizures will be analyzed for both treatment groups (ZX008 0.2 mg/kg/day and ZX008 0.8 mg/kg/day) comparing independently with placebo, using the same methods employed for the  $\geq 50\%$  reduction from baseline endpoint.
- The proportion achieving a 100% reduction from baseline in convulsive seizures, i.e., seizure-freedom, will be analyzed for both treatment groups (ZX008 0.2 mg/kg/day and ZX008 0.8 mg/kg/day) comparing independently with placebo, using the same methods employed for the  $\geq 50\%$  reduction from baseline endpoint.
- The proportion of subjects with near seizure freedom during the T+M period. Near seizure-freedom will be defined as having 0 or 1 seizures leading to a drop in the T+M period. These are additional secondary endpoints. Groups will be compared using the same methods employed for the  $\geq 50\%$  reduction from baseline endpoint.

A second response curve will be generated in which subjects who experience an increase in seizure frequency will be represented on the curve at horizontal axis at the position representing their increase in seizure frequency. Increases in seizure frequency will be represented to the left of the vertical axis on the figure.

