- Protocols 1501 and 1502 state that the longest interval between convulsive seizures will be analyzed using a log-rank test. However, further considerations of this endpoint suggest that while the first seizure-free interval may be subject to independent censoring, the second and later seizure-free intervals are subject to dependent censoring. Moreover, the last seizure-free interval is subject to intercept sampling, hence a longer seizure-free interval is more likely to be censored. Finally, the number of seizures or seizure-free intervals is informative about the underlying distribution, as subjects at a higher risk of experiencing recurrent events are likely to have shorter and hence more seizure-free intervals during the 84 day treatment period. Thus, a simple analysis comparing medians of the largest seizure free intervals was proposed.
- Responder analyses – Protocols 1501 and 1502 include a  $\geq 40\%$  response analysis as one of the key secondary endpoints. It was decided to not include this endpoint as the  $\geq 50\%$  response analysis is considered clinically meaningful.
- An analysis of the percentage of subjects who achieve a 25% reduction in seizures was added. The number of subjects whose seizures worsen during the study will be included, along with the percentage of worsening.
- The Protocol states that the BRIEF rating scale will be used to evaluate cognition in children aged 2-18. The BRIEF-P will be used for children aged 2-4, and the BRIEF will evaluate children aged 5-18.
- The protocol included the exploratory objective to compare the ZX008 0.2 mg/kg/day and ZX008 0.8 mg/kg/day doses on primary, secondary, safety, and PK endpoints. Comparisons between doses were not made using inferential statistics.
- The protocol states that subjects will enter information daily into the diary; in some cases, data could not be entered directly into the diary and had to be entered via the DCR process. These data were analyzed in the same manner as data entered directly.
- An analysis of the percentage of subjects who achieve a 100% reduction (near seizure-free) in seizures was added. The number of subjects whose seizures worsen during the study will be included, along with the percentage of worsening.

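### Study 2 SAP: near seizure-freedom is analysed on drop seizures but defined elsewhere on convulsive seizures, and the count has no exposure rule

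*SAP*

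**What the plan says.** All references are to the Study 2 SAP.

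- **Objectives (Section 2.2).** The list of additional secondary objectives includes "near seizure-free (ie, at most 1 convulsive seizure").
- **Endpoint list (Section 4).** The corresponding entry begins "The proportion of subjects with at most 1". It goes on to specify convulsive seizures during T+M, and it stands on a separate line from 100% reduction.
- **Analysis (Section 8.2.2, Responder Analyses).** "Near seizure-freedom will be defined as having 0 or 1 seizures leading to a drop in the T+M period". The three bullets before it (25%, 75% and 100% reduction) all concern convulsive seizures. Groups are to be compared as for the 50% responder endpoint.
- **Changes from the protocol (Section 12).** "An analysis of the percentage of subjects who achieve a 100% reduction (near seizure-free) in seizures was added".

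The following provisions bear on exposure:

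- The mITT population (Section 5.3) takes dosed subjects "for whom at least one week of diary data are available".
- Section 6.4 assumes that the planned duration "of T+M for Study 1 and Study 2 subjects is 14 weeks (98 days"). Section 6.5 ends each subject's T+M period at the end of study or end of treatment visit.
- Convulsive seizure frequency (Section 8.1) has as its denominator "Total number of days in the T + M period with nonmissing diary data". The near seizure-freedom rule has no denominator.
- On dropout, Section 6.4 reports: "The rates of dropout in the pivotal trials was 7.56% (9/119) in Study 1".

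**The concern.** Section 8.2.2 is the text that a programmer would implement, and it counts a class of seizure that the objective and the endpoint list do not. Drop seizures as a class are neither defined nor used anywhere else in the Study 2 SAP, so the document gives no way to map one rule onto the other. The responder set then depends on which section is followed, and that choice could be made after unblinding.

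The second weakness is that a raw count favours short observation. A subject who withdraws in the second week has had far less time to accumulate a second seizure than one followed for 14 weeks, yet both are judged against the same threshold. Section 6.4 itself warns that dropout may be related to response and that differential dropout may affect inference on the primary endpoint. Its two remedies, S1 and S2, do not reach this endpoint. S1 is written for convulsive seizure frequency, and the S1 and S2 tables in the Section 15 index (14.2.15.12 to 14.2.15.15) all report convulsive seizure frequency.

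**Working it through.** **1. The definitions applied to the same child**

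| Child during T+M | Section 8.2.2 | Sections 2.2 and 4 |
|---|---|---|
| Several convulsive seizures, none with a drop | success | failure |
| No convulsive seizure, two or more non-convulsive drop seizures | failure | success |

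The second row arises only if some drop seizures are not convulsive. The SAP lists the seizure types of neither class, so this can be neither confirmed nor excluded. A child with exactly one convulsive seizure is near seizure-free under Sections 2.2 and 4 but does not have the 100% reduction that Section 12 attaches to the term.

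**2. The plan's own figure**

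Dropout in Study 1: 9/119 = 0.0756, which reproduces the stated 7.56%. In an arm of 40 this is 40 × 9/119 = 3.03 subjects.

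**3. What one seizure means at different exposures**

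Rate per 28 days = 28 × count / days.

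- 7 days: 28 × 1/7 = 4.0
- 98 days: 28 × 1/98 = 0.29

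The ratio is 98/7 = 14. Both subjects score as near seizure-free.

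**4. Chance of qualifying without any drug effect**

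The documents give no seizure rates, so the rates here are assumptions. Seven days is the shortest exposure that mITT admits if the week of diary data is read as on-treatment data. For a Poisson count, P(0 or 1) = (1 + m) × exp(−m), with m = rate × days/28.

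| Assumed rate per 28 days | m in 7 days | P(0 or 1) in 7 days |
|---|---|---|
| 4 | 1 | 0.736 |
| 8 | 2 | 0.406 |
| 10 | 2.5 | 0.287 |
| 20 | 5 | 0.040 |

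At 4 per 28 days, with longer follow-up:

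- 14 days (m = 2): 0.406
- 28 days (m = 4): 0.092
- 49 days (m = 7): 0.007
- 98 days (m = 14): 0.00001

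The contrast depends on the model. For a negative binomial with dispersion 1, P(0 or 1) = 1 − (m/(1 + m))². At 4 per 28 days this gives 1 − (1/2)² = 0.750 in 7 days and 1 − (14/15)² = 0.129 in 98 days.

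**5. From dropouts to false successes**

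The expected number per arm is 3.03 × P(0 or 1), if dropout is spread evenly over the arms and all dropouts share one rate and one leaving time:

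- all leave at day 7, rate 4: 3.03 × 0.736 = 2.2
- all leave at day 28, rate 4: 3.03 × 0.092 = 0.3
- all leave at day 7, rate 20: 3.03 × 0.040 = 0.1

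**6. The 100% reduction endpoint**

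Dividing by diary days does not help here, because zero seizures over any number of days is a frequency of zero. At 4 per 28 days the Poisson chance of no seizure in 7 days is exp(−1) = 0.368.

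**The case against.** Several limits on the point are fair and stand.

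- **Section 12 is not a third operative rule.** It is a loose parenthesis in a list of changes. Sections 4 and 8.2.2 both keep 100% reduction and near seizure-freedom apart. There is one real conflict, Section 8.2.2 against Sections 2.2 and 4, plus a careless label.
- **Over-counting is not shown.** A reader might infer that ignoring convulsive seizures without a drop must inflate success. That holds only if every drop seizure is also convulsive, and the SAP does not say so.
- **Early dropouts are not all scored as successes.** Only those with 0 or 1 qualifying seizures before leaving are.
- **The large probabilities come from low rates and very early departure.** Rates of 4 and 8 per 28 days fall in the lowest of the SAP's own baseline categories (below 10, 10 to 50, above 50). The documents give no dropout times, so the figure of 3 per 40 counts dropouts, not false successes.
- **A bias towards ZX008 is hypothetical.** Differential withdrawal on active drug would be needed, and the documents give no dropout by arm.
- **The endpoint carries little formal weight.** It is an additional secondary endpoint, outside the six-step hierarchy of Section 6.3.

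None of this reconciles Section 8.2.2 with Sections 2.2 and 4, and none supplies an exposure rule.

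**Conclusion.** The contradiction is certain from the text: the analysis section counts a different class of seizure from the objective and the endpoint list. What can be claimed is misclassification in an unknown direction, not inflated success.

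The exposure gap is also certain from the text, but its size is conditional. At the Study 1 dropout rate, spread evenly, at most about 3 subjects in an arm of 40 are exposed to it. Under the assumed Poisson model the expected number of false successes runs from about 2 per arm (everyone leaves at day 7, at 4 seizures per 28 days) to well below 1 with later departure or higher rates. The documents do not support saying that the gap favours ZX008.

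The primary and key secondary tests, the familywise error rate and the sample size are untouched. The point should be corrected because the endpoint is to be tested and reported, and the correction needs only a change of wording.

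**What to change.** 1. In Section 8.2.2, replace the drop-seizure wording with convulsive seizures, so that the rule reads 0 or 1 convulsive seizures during T+M, in line with Sections 2.2 and 4.
2. In Section 12, describe 100% reduction and near seizure-freedom as two separate additions.
3. State that a subject who does not complete T+M to Day 99 ± 4 is scored as not near seizure-free, and apply the same rule to 100% reduction. Refer to the day window, which Section 6.2 already uses for treatment completers, and not to Visit 12: Section 6.5 gives the early termination visit that same number, so a rule worded as leaving before Visit 12 would not identify dropouts.

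A minimum number of diary days, or a sensitivity analysis with dropouts as failures, would also address the third item. Scoring non-completers as failures is the simplest and leaves no threshold to choose.

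The cost is SAP wording and a small programming change. The reported proportions may be slightly lower.

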### Change from Baseline in Non-Convulsive Seizure Frequency

Algorithms for calculating mean non-convulsive seizure frequency and percent change from baseline will follow the methods as described for the primary endpoint using a nonparametric ANCOVA to analyze the data, with ranks of the baseline non-CSFB as a covariate and ranks of non-CSFT+M as response,.

Change from baseline in non-convulsive seizures will be presented by seizure types (e.g., focal, generalized).

### Change from Baseline in Convulsive + Non-Convulsive Seizure Frequency

The change from baseline in convulsive + non-convulsive seizure frequency will be calculated as described for the primary endpoint, but considering both convulsive and non-convulsive seizures.

Algorithms for calculating mean convulsive and non-convulsive seizure frequency and percent change from baseline will follow the methods as described for the primary endpoint using a nonparametric ANCOVA to analyze the data, with ranks of the baseline convulsive + non-CSFB as a covariate and ranks of convulsive + non-CSFT+M as response,

### Incidence of Rescue Medication Usage

Use of rescue medication is recorded on the daily diary. In the event of prolonged seizures or status epilepticus, rescue medication is administered according to each subject's personalized regimen consisting of one or more medications. If the first rescue administration does not control the seizures, a second or even third round might be administered. They second and third round might use different medications or different doses than the first round of rescue meds.

Rescue medication will be summarized by treatment group and by active treatment vs. Placebo for the following:

- The number of days rescue medication was taken (normalized to 28 days) will be summarized separately for the Baseline, T+M periods and change from baseline by the mean (SD) as well as the median and range. Multiple medications taken on the same day will be counted once for that

This document is confidential.

## Statistical Analysis Plan

Sponsor: Zogenix International Limited; Protocol No.: ZX008 Study 2 (ZX008-1501 and ZX008-1502)

---

day. The ZX008 group will be compared to the placebo group using a rank ANCOVA analogous to that described in Section 8.1 Primary analysis. Specifically, the rank ANCOVA will use the ranks of rescue medication frequency during T+M as the response, and will incorporate treatment group as a factor and the ranks of rescue medication frequency during Baseline as a covariate.

- The number of medications used per episode will be summarized using similar descriptive statistics as above. Rescue medications related to an episode of SE are considered to be all rescue administered on the day of the SE (or seizure lasting > 10 min). If more than one episode of SE or a seizure lasting > 10 min occurred in a single day, the rescue medication for that episode is all rescue administered after the seizure until the start time of the next prolonged seizure.

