## 6. General Aspects for Statistical Analysis

### 6.1. General Methods

All statistical analyses will be performed using SAS statistical software (Version 9.4 or later).

Study 2 summaries will be presented by treatment group (Placebo, ZX008 0.2 mg/kg/day, ZX008 0.8 mg/kg/day).

Continuous data will be summarized using descriptive statistics including means, standard deviations, medians, lower and upper quartiles, minimum and maximum values. Categorical variables will be summarized with frequencies and percentages. Confidence intervals will be calculated for key parameters or estimates as warranted.

Two-sided statistical significance testing ( $\alpha = 0.05$ ) comparing each active treatment to placebo will be performed for the primary and secondary endpoints as described below, unless otherwise noted.

All relevant collected subject data will be included in listings. All subjects entered into the database will be included in data listings.

Unless otherwise specified in the subsequent sections, in the event of multiple assessments at a given planned time point, the latest collected value will be used for the summarization.

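### The rescue-medication test names a single ZX008 group against placebo and omits age group, so it is unclear that each dose is tested independently as the objective requires

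*SAP*

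**What the plan says.** Study 2 SAP, Section 2.2, puts the incidence of rescue-medication usage under this objective: "To demonstrate that the ZX008 0.2 and 0.8 mg/kg/day dose groups are (independently) superior to placebo on the following endpoints". Section 4 repeats it in the endpoint list: "ZX008 0.2 and 0.8 mg/kg/day dose groups compared independently versus placebo on the".

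The analysis is specified only in Section 8.2.2, Incidence of Rescue Medication Usage. The lead-in is "Rescue medication will be summarized by treatment group and by active treatment vs. Placebo for the following". The test is "The ZX008 group will be compared to the placebo group using a rank ANCOVA analogous to that described" in Section 8.1. The response is then given as the ranks of rescue-medication frequency during T+M, and the model "will incorporate treatment group as a factor and the ranks of rescue medication frequency during Baseline as a covariate". Neither dose is named, the number of treatment levels is not given, and age group is not mentioned.

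Section 6.3.3.5 of the Study 1 SAP has the same test wording, with a cross-reference to its own primary analysis section.

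**The concern.** The objective asks two questions, one per dose, and the analysis sentence describes one comparison. Read literally, it answers neither. A pooled contrast averages a low and a high dose. It can miss an effect of 0.8 mg/kg/day that is diluted by a weak low dose, and a significant result could be read as support for 0.2 mg/kg/day even if that dose does nothing.

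Even if a pooled test was never intended, two programmers could follow this text and produce different p-values for the same pre-specified test, and the choice between them could be made after the data are seen.

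The missing age term is a separate, smaller inconsistency. Randomisation was stratified by age (under 6 years, 6 years and over), and the primary ANCOVA and the neighbouring hospitalisation and status epilepticus tests all use it.

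**Working it through.** **1. Which contrast does the text fix?** All references are to the Study 2 SAP.

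Pointing to per-dose contrasts:
- Section 6.1 sets the general rule as two-sided testing "comparing each active treatment to placebo will be performed for the primary and secondary endpoints as described below, unless otherwise noted".
- Section 6.1 also uses treatment group to mean three groups: "Study 2 summaries will be presented by treatment group (Placebo, ZX008 0.2 mg/kg/day, ZX008 0.8 mg/kg/day").
- The rescue test is modelled on Section 8.1, where the ANCOVA has treatment at three levels.

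Leaving a pooled contrast open:
- The test sentence has one ZX008 group, in the singular.
- The lead-in sets an active-versus-placebo grouping beside the by-treatment-group one.
- Sensitivity analysis S1 in Section 6.4 writes the treatment term with two levels, placebo and ZX008, so a treatment term does not always mean three levels in this SAP.
- The responder and status epilepticus sections also describe treatment with two labels, but each goes on to say that both doses are compared with placebo. The rescue section does not.

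The text permits both readings. It does not fix either.

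**2. What pooling would cost, on the plan's own sizing figures.** Section 2.5 gives a difference of 40 percentage points, SD 55, 40 per arm, two-sided 5% and 90% power, all for the primary endpoint.

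- Reproduction: n per arm = 2 × (1.960 + 1.282)² × 55² / 40² = 39.7, so 40. The stated figure reproduces. Noncentral-t power at 40 per arm is 89.5%.
- 0.8 mg/kg/day against placebo, 40 v 40: standard error = 55 × √(1/40 + 1/40) = 12.30; noncentrality = 40 / 12.30 = 3.25; power 89.5%.
- Pooled, 80 v 40: standard error = 55 × √(1/80 + 1/40) = 10.65. If the 0.2 dose has a fraction f of the 0.8 effect, the pooled difference is (40 + 40f) / 2.

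| f | Pooled difference | Noncentrality | Pooled power | 0.2 dose alone |
|---|---|---|---|---|
| 0 | 20 | 1.88 | 46% | 5% |
| 0.25 | 25 | 2.35 | 64% | 13% |
| 0.5 | 30 | 2.82 | 80% | 36% |
| 0.75 | 35 | 3.29 | 90% | 67% |
| 1 | 40 | 3.76 | 96% | 89.5% |

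This assumes that rescue use has the same standardised effect as the primary endpoint, and it uses a t-test in place of the rank ANCOVA.

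**3. Simulation of the rank ANCOVA itself.** Overdispersed counts of rescue days, 40 per arm, 25% under 6 years, an age effect of 0 or 0.7 on the log scale, and 4,000 runs per scenario (Monte Carlo standard error at most √(0.25/4000) = 0.8 points). Every effect size is an assumption. The three contrast columns use the model without age; ranges run over the two age effects.

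| Log-rate reduction, 0.2 / 0.8 | Pooled rejects | 0.8 contrast rejects | 0.2 contrast rejects |
|---|---|---|---|
| 0 / 0 | 5.1–5.4% | 4.7–5.4% | 4.9–5.1% |
| 0 / 0.5 | 14–15% | 33–36% | 5–6% |
| 0 / 0.8 | 26–27% | 65–68% | 5–6% |
| 0 / 1.0 | 37–39% | 83–86% | 6% |
| 0.4 / 0.8 | 56–58% | 67–70% | 25–26% |

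With an inactive low dose, the pooled test loses about 19 to 47 points against the 0.8 contrast (33.2 − 14.3 = 18.9; 86.0 − 39.1 = 46.9).

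**4. Leaving out age.** With no treatment effect, the per-dose contrasts reject in 4.7–5.4% of runs without age and 5.0–5.3% with it. The largest gain in power from adding age is 1.0 point (68.0% to 69.0%).

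**The case against.** The strongest reply is that the per-dose reading is the natural one. Section 6.1 requires each active treatment to be compared with placebo, Section 8.1 has a three-level factor, and where this SAP clearly combines the doses it says so (Section 10, for safety). Singular ZX008 or active is also the author's shorthand in sections that are plainly per dose, such as the responder and status epilepticus sections. The active-versus-placebo phrase in the lead-in describes summaries, not the model. Most of this stands, and it means that a pooled test has not been shown to be the plan. It does not close the question: the general rule defers to what is described below it, what is described is one group, and those other sections state the per-dose comparisons that this one leaves out.

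On age, the rank ANCOVA in Section 8.1 restates only the baseline and response ranks, and an analogous model may carry age over. That is fair, and the numerical effect is negligible in the simulation.

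The power figures borrow the primary endpoint's sizing or use assumed rates, and they matter only if the test is pooled. That stands too.

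A reader might infer that the plan fixes a pooled test, that the 0.2 mg/kg/day question goes untested, or that omitting age prevents a per-dose conclusion. The documents support none of these: a three-level reading is available and gives both contrasts directly, and age bears only on precision.

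**Conclusion.** The wording is ambiguous and should be corrected. The rescue-medication test does not match the objective and endpoint it serves. A per-dose analysis is permitted but not stated, and a pooled one is not excluded. If pooled, the test could not support a claim for either dose. That conclusion is logical and does not depend on any effect size.

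The size of the loss cannot be derived from the SAP, which gives no rescue-use rates. The illustrations run from a 43-point loss for the 0.8 mg/kg/day question (89.5% to 46%, low dose inactive) to a slight gain if the two doses are equally effective (89.5% to 96%). The age omission is a consistency point worth about 1 point of power at most under the simulated conditions.

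Severity is low. Rescue medication is an additional secondary endpoint outside the six-step hierarchy in Section 6.3, so no primary or key secondary conclusion is affected.

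**What to change.** In Section 8.2.2 of the Study 2 SAP, replace the test sentence and the model list with wording such as: each ZX008 dose group (0.8 and 0.2 mg/kg/day) will be compared with placebo by separate contrasts from one rank ANCOVA of T+M rescue-medication days per 28 days, with treatment group (three levels) and age group (<6, ≥6 years) as factors and the ranks of Baseline rescue-medication days per 28 days as covariate. Add that any pooled ZX008 result is descriptive.

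The cost is one sentence, one model statement and one degree of freedom for age. No new data are needed. The Study 1 wording has the same defect, but the Study 2 SAP (Section 2.3) records Study 1 as reported in September 2017. There it is enough to state which contrast was run.
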